10.3 Control of Systematic Error and Bias

The study will be conducted under a common protocol for each investigational site with the intention of pooling the data for analysis. Every effort will be made to promote consistency in study execution at each investigational site.

10.4 Missing Data and Imputation Methods

Every effort is to be made to keep all missing data, particularly the Final Follow-Up, to a minimum. Some data may be missing, mainly due to lost-to-follow-up subjects. The primary analysis will be data as observed. Sensitivity analysis will be performed.

10.5 Definition of Populations

10.5.1 Screened

Screened subjects are all subjects considered for participation in the study, whether or not they sign informed consent.

10.5.2 Screen Failure

Screen failure subjects are all subjects considered for participation in the study, who failed to meet inclusion criteria or met exclusion criteria. Patients can be screen failed based on general or procedure criteria. These patients may or may not have signed an informed consent form.

10.5.3 Enrolled

An eligible patient is considered enrolled once informed consent is obtained, index procedure is complete, and all inclusion criteria is confirmed.

10.5.4 Completed

Completed subjects are all subjects who were enrolled and completed the study follow-up or were known to have died prior to the follow-up timepoint are considered completed. The completed subject metric will be provided for Final Follow-Up.

10.5.5 Early Termination

Early termination subjects are all subjects who were enrolled but did not complete follow-up and were not known to have died are considered early termination subjects. The early termination subject metric will be provided for Final Follow-Up.

10.6 Definition of Analysis Populations

10.6.1 Intent to Treat Sample

As the primary analysis, all performance and safety outcome measures will be analyzed under the intent-to-treat (ITT) principle. Under this principle, the ITT sample includes all subjects who are enrolled. This population is the primary analysis population.

10.7 Interim Analysis

No interim analyses are planned for the purpose of stopping the study early. Interim analysis may be performed for regulatory submission or publication of study results. No adjustments will be made to the confidence bounds for the final analysis.

10.8 Statistical Analysis of Primary Efficacy Endpoint

The primary efficacy endpoint is the rate of aneurysm occlusion at Final Follow-Up per Raymond-Roy classification. The proportion of subjects assessed as Raymond-Roy I or II will be provided along with the corresponding 95% confidence interval.

10.9 Statistical Analysis of Primary Safety Endpoint

The primary safety endpoints are the following:

- SAEs up to 24 hours post-procedure
- Device-related SAE up to 7 days or discharge

The proportion of subjects experiencing each event will provided along with the corresponding 95% confidence interval.

10.10 Secondary Statistical Analysis

The secondary efficacy and safety endpoints will be assessed via proportions based on the endpoint criteria and 95% confidence intervals will be presented. Survival

estimates will also be utilized to evaluate the time-to-event using Kaplan-Meier methodology for deaths through 365 days. With the date of procedure set at day 0, any event occurring on or before day 365 will be included.

10.11 Analysis of Adverse Events

All adverse events will be summarized by showing the number and percent of subjects which report the event. Events will also be reported by relationship to the procedure or device. Adverse events judged as probably or definitely related to the SMART COIL System will be analyzed as device-related.

10.12 Imaging Outcomes Analysis

Aneurysm occlusion outcomes as assessed by the core lab will be evaluated for subjects that have both a DSA and MRA at follow-up. A sensitivity and specificity analysis will be conducted to evaluate the ability of MRA to detect residual flow in the coiled aneurysms.

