cases of intra-procedural thrombosis treated with IV Absciximab occurred. There were three patient deaths of presenting subarachnoid hemorrhage and one case of delayed procedure related mortality (remote hemorrhage in stent assisted coiling case). The author reported that there was no change in the baseline modified Rankin score (mRS) for the remaining patients. In addition, the 6-month follow-up was available in 39/75 patients and showed complete aneurysm occlusion with no remnants in 32 patients and small neck remnants in 7 patients (under observation). The author concluded that the SMART (Penumbra, Inc.) coil system was safe, easy to use, and effective especially in the treatment of otherwise difficult to treat very small intracranial aneurysms [33].

A retrospective cohort study was recently completed by Sokolowski et al. to assess the angiographic outcomes at interim follow-up after aneurysm embolization with SMART coils between June 2016 and August 2017 [38]. Baseline data and follow-up angiographic outcomes using the modified Raymond-Roy classification (MRRC) were reported from 33 patients with 34 aneurysms. The initial mean coil packing density was 26%, and the initial MRRC was I, II, IIIa, and IIIb in 24%, 26%, 35%, and 15%, respectively. The overall complication rate was 12%. At last follow-up (mean duration 7.7 ± 3.2 months), the retreatment rate was 14.7%, the MRRC was I, II, IIIa, and IIIb in 62%, 26%, 3%, and 9%, respectively. The authors reported that the majority of residual aneurysms after the initial embolization procedure would progress to complete or near-complete occlusion at interim follow-up [38]. In conclusion, they reported that the SMART coil was efficacious for the treatment of appropriately selected aneurysms and had an acceptable risk profile.

The SMART Registry is a prospective, multicenter registry sponsored by Penumbra, Inc. to assess the treatment of intracranial aneurysms and other neurovascular abnormalities. For eligibility, the intervention must have implanted at least 75% SMART COIL, Penumbra Coil 400TM, and/or Penumbra Occlusion Device (POD[®]) (Penumbra, Inc.). Study endpoints included retreatment through one-year follow-up, procedural device-related serious adverse events (SAE), occlusion status at immediate post-procedure, and at one-year follow-up.

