The objective of this study is to demonstrate the safety and efficacy of the Penumbra SMART COIL System including WAVE Extra Soft as a fill and finish coil in the treatment of intracranial aneurysms. Imaging will be analyzed by an independent core lab to assess aneurysm occlusion rates and perform a comparative analysis between imaging modalities.

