6.2 Study Visits

Subjects enrolled in this study will follow the visit schedule below and will continue to receive routine practice/ standard of care treatment. Procedure is day 0 for determining follow-up visit dates.

- Screening & Baseline
- Procedure
- 7 Day and/or Discharge
- 1 Year Follow-Up ± 90 Days

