6.9 Final Follow-Up (1 Year \pm 90 Days)

All assessments are to be conducted in accordance with routine care at each participating hospital, the following data will be collected but is not limited to:

- Aneurysm occlusion grade
- Vital signs
- mRS
- Retreatment information
- Adverse event review
- Angiography*

*Angiography will be performed per institutional standard of care. DSA, CTA, or MRA are accepted for imaging modality. Images will be sent to an Imaging Core Laboratory to make a final determination on aneurysm occlusion rate. If both DSA and MRA are available, then both imaging modalities should be submitted for Core Laboratory review.

Table 2: Schedule of Assessments

ACTIVITY	SCREENING & BASELINE	PROCEDURE	7-DAY AND/OR DISCHARGE	FINAL FOLLOW-UP (1 YEAR ± 90 DAYS)
Written Informed Consent	X ¹			
Demographics	X			
Medical History	X			
Vitals	X		X	X
mRS	X ²		X	X
Hunt & Hess	X ³			
Procedure		X ⁴		
Occlusion Grading		X		X ^{4,5,6}
Adverse Event Review		X	X	X

¹ For sites in North America, patients who have had an index procedure with SMART Coils and all inclusion/exclusion confirmed, may be consented up to 2 days post procedure but prior to discharge

² Baseline mRS is based on subject status prior to the index procedure

³ For patients presenting with SAH

⁴ Imaging should be uploaded into Image Management System within 14 days

⁵ Occlusion Grading and other datapoints will be collected if retreatment occurs prior to study exit

⁶ If both DSA and MRA are performed as part of standard of care follow-up, then both imaging modalities should be submitted for Core Laboratory review

7. Investigator Responsibilities

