8.3 Imaging Outcomes Analysis

DSA is the reference standard imaging modality for aneurysm assessment after coiling, but MRA imaging is safer for patients and less expensive. Therefore, an imaging outcomes analysis will assess how successfully MRA scans detect residual aneurysm blood flow at final follow-up as compared to DSA scans, based on sensitivity, specificity, and related summary measures.

For each of Raymond-Roy Class II to III (any residual flow), Class II (residual neck), and Class III (residual aneurysm) at the time of final follow-up, the following statistics will be reported using the ITT population and core lab data:

- **Sensitivity:** The proportion of true positives (patients belonging to each of the three Raymond-Roy groups above on DSA) that are correctly identified as such on MRA as well. The percentages of patients assessed as each of Raymond-Roy (1) Class II to III, (2) Class II, and (3) Class III on MRA and DSA out of patients with the same Raymond-Roy group assessed on DSA at the time of final follow-up will be computed.
- **Specificity:** The proportion of true negatives (patients not belonging to each of the three Raymond-Roy groups above on DSA) that are correctly identified as such on MRA as well. The percentages of patients assessed as each of Raymond-Roy (1) Class I, (2) Class I or Class III, and (3) Class I to II on MRA and DSA out of patients with the same Raymond-Roy group assessed on DSA at the time of final follow-up will be computed.
- **Positive likelihood ratio (LR):** Sensitivity divided by (1 - Specificity).
- **Negative likelihood ratio (LR):** (1 - Sensitivity) divided by Specificity.
- **Cohen's κ :** Summary measure of agreement between DSA and MRA in detecting each of Raymond-Roy Class II and III, Class II, and Class III.

As a secondary comparison, this analysis will be repeated using each of Meyers Consensus Grading Scale Grades 1 to 5 (any residual flow), Grade 1 (90% or greater aneurysm occlusion), Grade 2 (70-89% aneurysm occlusion), Grade 3 (50-69% aneurysm occlusion), Grade 4 (25-49% aneurysm occlusion), and Grade 5 (Less than 25% aneurysm occlusion).

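### The MRA-versus-DSA accuracy analysis sets no limit on the time between scans and does not exclude retreatment between them, so real change in the aneurysm can be scored as MRA error

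*Combined protocol and SAP*

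**What the plan says.** Protocol Section 4, like the synopsis, says that the core lab's reading of images will serve to "assess aneurysm occlusion rates and perform a comparative analysis between imaging modalities". The SAP Overview repeats this as an analysis of the sensitivity and specificity of MRA against DSA.

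On who enters the comparison, protocol 10.12 says: "Aneurysm occlusion outcomes as assessed by the core lab will be evaluated for subjects that have both a DSA and MRA at follow-up". No other condition is given.

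On timing, protocol 6.2 lists the visit as "1 Year Follow-Up ± 90 Days". On acquisition, protocol 6.9 says: "Angiography will be performed per institutional standard of care. DSA, CTA, or MRA are accepted for imaging modality". On submission it says: "If both DSA and MRA are available, then both imaging modalities should be submitted for Core Laboratory review".

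SAP 8.3 names DSA as the reference standard and asks "how successfully MRA scans detect residual aneurysm blood flow at final follow-up as compared to DSA scans". Sensitivity and specificity are the shares of DSA-positive and DSA-negative patients "correctly identified as such on MRA as well". Likelihood ratios and kappa follow from the same cross-tabulation.

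The rule that a retreated patient is modelled as Class III, or as recanalized, is written into SAP 8.1 and 8.2. SAP 8.3 does not mention retreatment, although Table 2 of the protocol foresees retreatment before study exit.

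**The concern.** Scoring every disagreement as an MRA error is sound only if both scans show the aneurysm in the same state. The protocol gives reasons to doubt that across a gap of weeks or months. Its Introduction cites a small retrospective SMART coil cohort whose authors reported that "the majority of residual aneurysms after the initial embolization procedure would progress to complete or near-complete occlusion at interim follow-up", and it cites a 15.4% recanalization rate for bare platinum coils in a trial with a 24-month endpoint. Recanalization and progressive thrombosis are themselves a secondary endpoint of this study.

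Retreatment is the plainest case. An MRA correctly shows a residual, the aneurysm is retreated, and a later DSA shows Class I. SAP 8.3 as written counts that MRA as a false positive. If someone instead carried the Class III rule over from SAP 8.1 and 8.2 to both reads, the same pair would become an agreement that no reader saw. The plan does not say which applies, and neither result measures MRA accuracy.

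What is at stake is the interpretation of the accuracy table. The problem is separate from the question of which patients get both scans, and it would remain if every patient had both.

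**Working it through.** **The plan's own figures.** The documents give no expected number of pairs and no precision for the MRA-DSA comparison. The nearest stated figure concerns the primary endpoint: 641/720 = 89.0%, half-width 1.96 × √(0.890 × 0.110 / 720) = 2.3 points, so 86.7% to 91.3%. This reproduces the stated 87% to 91%, but it does not size the imaging comparison.

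**Window.** 365 − 90 = day 275 and 365 + 90 = day 455, so the width is 180 days. This is the largest possible gap if the visit window is applied to both scans. Protocol 10.12 says only that both were done at follow-up.

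**Direction for a single real change between scans.**

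| Change between scans | MRA first | DSA first |
|---|---|---|
| Residual closes or is retreated | MRA+, DSA−: specificity falls | DSA+, MRA−: sensitivity falls |
| Occluded aneurysm recurs | MRA−, DSA+: sensitivity falls | DSA−, MRA+: specificity falls |

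**Size under assumed change (illustration only).** Let r be the share with residual flow at the first scan, c the probability that a residual closes before the second scan, and n the probability that an occluded aneurysm reopens. For a perfect MRA:

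- DSA first: sensitivity = 1 − c; specificity = 1 − n.
- MRA first: sensitivity = r(1 − c) / [r(1 − c) + (1 − r)n]; specificity = (1 − r)(1 − n) / [(1 − r)(1 − n) + rc].

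With c = n = 5% and DSA first, both are 95%. With MRA first and r = 20%, sensitivity = 0.19 / (0.19 + 0.04) = 82.6% and specificity = 0.76 / (0.76 + 0.01) = 98.7%. All values of c, n and r are assumptions:

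| c = n | DSA first, sens/spec | MRA first, r = 20% | MRA first, r = 40% |
|---|---|---|---|
| 0% | 100/100 | 100/100 | 100/100 |
| 2% | 98/98 | 92.5/99.5 | 97.0/98.7 |
| 5% | 95/95 | 82.6/98.7 | 92.7/96.6 |
| 10% | 90/90 | 69.2/97.3 | 85.7/93.1 |

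An MRA that is truly 90/90, with DSA first and 5% change, appears as 0.95 × 0.90 + 0.05 × 0.10 = 86% on both measures.

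**Retreatment alone.** The registry cited in protocol Section 1 gives 6/157 = 3.8% through one year. Suppose the same rate in the paired subset, and let f (assumed) be the fraction of those retreatments that fall between a positive DSA and a later MRA showing full occlusion. A perfect MRA's apparent sensitivity is 1 − 0.0382 × f / prevalence, where prevalence is the assumed share of DSA-positive pairs.

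| f | Prevalence 40% | Prevalence 20% |
|---|---|---|
| 25% | 97.6% | 95.2% |
| 50% | 95.2% | 90.4% |
| 100% | 90.4% | 80.9% |

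The last row is an extreme, because the registry rate accumulates over the whole year and only retreatments between the two submitted scans matter.

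**The case against.** The best defence is that the plan intends one visit. SAP 8.3 speaks of the time of final follow-up, Table 2 puts both modalities in one visit column, and ±90 days is naturally read as tolerance on the date of that visit. Many pairs may be close together. That is fair, and it makes a 180-day gap a theoretical maximum. It does not close the gap, because nothing ties one scan to the other inside the window. SAP 8.4 also expects additional follow-up DSA, MRA and CTA scans, with no rule for choosing among them.

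Second, a rule may sit in the Core Lab Charter (protocol 11.1) or in the image collection instructions (protocol 7.5), neither of which is available here. The protocol describes the charter as governing image review. Neither document says that it decides which pairs enter the accuracy analysis. The point is therefore about the protocol and SAP as written.

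Third, the comparison is not a listed primary or secondary endpoint, and protocol 10.1 makes all analyses descriptive. This limits the consequence. It does not remove it, because the comparison is part of the study objective and has its own SAP section.

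**Conclusion.** The point stands for the MRA-DSA comparison. Following the stated rule would let real change or treatment effect count as MRA error, and no visible text prevents it. The figures above rest on assumed change rates, prevalences and scan order. They show the mechanism and do not forecast the bias.

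Three stronger readings are tempting and are not supported.

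- **A reader might take a change rate from the small cohort in protocol Section 1.** Class I rose there from 24% to 62% over a mean of 7.7 months. If no Class I result was lost, 38/76 = 50% of residuals closed, and −ln(1 − 0.50)/7.7 is about 9% per month. With a perfect MRA done first and 40% residual, that rate would put apparent specificity at 78.4% after 180 days. But the cohort has 34 aneurysms, the rise is measured from the procedure and not near one year, and 14.7% (about 5 of 34) were retreated. Class I went from about 8 to 21. If all 5 retreated aneurysms were among the new Class I results, closure without retreatment is 8/26 = 31%, or about 4.8% per month. The cohort shows that status changes. It gives no usable rate for days 275 to 455.
- **A reader might infer that the bias always lowers specificity, or always lowers sensitivity.** It depends on scan order, which the documents do not give.
- **A reader might extend the problem to the primary results.** The primary endpoints and the sample size do not use MRA-DSA pairs in this way and are unaffected.

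**What to change.** In protocol 10.12 and SAP 8.3:

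1. Exclude from the accuracy analysis any pair with retreatment of the target aneurysm between the two scans.
2. Restrict the main accuracy analysis to pairs obtained within a short interval that is fixed before database lock, so that the limit is not chosen after seeing the results. Thirty days is one reasonable value, but it is a choice and not a figure from the documents.
3. Report the distribution of the interval and the order of the scans.
4. Show all pairs without intervening retreatment, at any interval, as a supplementary analysis.
5. State that the Class III retreatment rule of SAP 8.1 and 8.2 is not applied to the MRA-DSA reads. Otherwise a patient retreated before both scans would also be turned into an automatic agreement.

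The cost is a wording change in both documents, fewer pairs, and less precise estimates in the main accuracy table. If most pairs are close together, little is lost. Before adopting the rule, confirm that both dates are captured: protocol 6.9 lists retreatment information without naming a date, and scan dates are only implied by the 14-day upload rule in protocol 7.5.

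### MRA accuracy is estimated only in patients who had both DSA and MRA in routine care, with no check or correction for selective use of DSA

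*Combined protocol and SAP*

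**What the plan says.** Protocol 10.12 states that core-lab occlusion outcomes "will be evaluated for subjects that have both a DSA and MRA at follow-up", in order to "evaluate the ability of MRA to detect residual flow in the coiled aneurysms".

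Paired imaging is not assigned. On the final visit Protocol 6.9 says: "Angiography will be performed per institutional standard of care. DSA, CTA, or MRA are accepted for imaging modality". A footnote to the schedule of assessments (Table 2) adds: "If both DSA and MRA are performed as part of standard of care follow-up, then both imaging modalities should be submitted" for core-lab review.

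SAP 8.3 gives the rationale: "DSA is the reference standard imaging modality for aneurysm assessment after coiling, but MRA imaging is safer for patients and less expensive". Sensitivity is the proportion of DSA-positive patients "that are correctly identified as such on MRA as well". Specificity is the mirror image, and likelihood ratios and kappa follow. This is done for Raymond-Roy Class II to III, Class II alone and Class III alone, and repeated for the Meyers grades. SAP 8.3 names the ITT population and does not repeat the both-scans restriction.

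The imputation analyses in SAP 12 cover only the primary effectiveness and primary safety endpoints. The comparison of modalities belongs to the stated study objective (Protocol 4, SAP 1) but is not a primary or secondary endpoint (Protocol 4.2).

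**The concern.** A diagnostic accuracy table built only from patients who received both the index test and the reference test is unbiased for all patients with the index test only if having the reference test does not depend on the index result, directly or through something related to it. Here that dependence is left to routine care. The plan does not report how often DSA accompanied each MRA result, does not say that the order of the scans or the reason for the second one is recorded, does not compare paired with unpaired patients, and applies no correction.

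SAP 8.3 motivates the comparison by the safety and cost of MRA, so a reader will use the result to judge whether MRA can stand in for DSA at follow-up. If DSA were concentrated among MRA-positive patients, the raw table would make MRA look better at ruling out residual flow than it is, and worse at ruling it in. Both errors matter for that judgement.

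**Working it through.** **No planned figure to reproduce.** The documents give no expected accuracy, number of paired scans or precision for this analysis. All accuracy and verification rates below are assumptions, used to show the range.

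**Formulas.** Let Se and Sp be the true values, v1 the share of MRA-positive patients who have DSA, and v0 the share of MRA-negative patients who have DSA. Suppose DSA depends only on the MRA result.

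- Raw sensitivity = Se·v1 / [Se·v1 + (1 − Se)·v0]
- Raw specificity = Sp·v0 / [Sp·v0 + (1 − Sp)·v1]

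Prevalence cancels. Only the ratio v1/v0 matters: it multiplies the odds of sensitivity and divides the odds of specificity.

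**Any residual flow (Class II to III), true Se 80%, Sp 90%.** For example, at 80%/20%: sensitivity = 0.64/(0.64 + 0.04) = 94.1%; specificity = 0.18/(0.18 + 0.08) = 69.2%.

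| v1 / v0 | Raw Se | Raw Sp | LR+ | LR− |
|---|---|---|---|---|
| equal | 80.0% | 90.0% | 8.0 | 0.22 |
| 50% / 40% | 83.3% | 87.8% | 6.8 | 0.19 |
| 60% / 30% | 88.9% | 81.8% | 4.9 | 0.14 |
| 80% / 20% | 94.1% | 69.2% | 3.1 | 0.09 |
| 20% / 40% | 66.7% | 94.7% | 12.7 | 0.35 |

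LR+ = Se/(1 − Sp) and LR− = (1 − Se)/Sp, as in SAP 8.3. The last row is the opposite pattern, and both errors change sign.

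**Class II alone.** Take an assumed true class mix of 60/29/11% (I/II/III). Assume MRA classifies true I as 90/8/2%, true II as 20/70/10% and true III as 5/15/80%. With no selection, Class II sensitivity is 0.70 and specificity 0.91.

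- DSA in 20/60/60% of MRA Class I/II/III: sensitivity = 0.70·0.6 / (0.20·0.2 + 0.70·0.6 + 0.10·0.6) = 0.42/0.52 = 0.81; specificity 0.81.
- DSA in 20/20/80%: sensitivity = 0.14/(0.04 + 0.14 + 0.08) = 0.54; specificity 0.94.

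So the direction for Class II alone depends on which MRA class leads to DSA. In both examples the Class II to III and Class III targets moved towards higher sensitivity and lower specificity.

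**Does a correction work?** Scale to the 720 patients expected at final follow-up (SAP 2), supposing for illustration that all have MRA, that 40% have residual flow, that true accuracy is 80%/90%, and that verification is 80%/20%.

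- All patients: MRA-positive 230.4 + 43.2 = 273.6; MRA-negative 57.6 + 388.8 = 446.4.
- With DSA: 184.32 true and 34.56 false positives; 11.52 false and 77.76 true negatives.
- Raw sensitivity = 184.32/195.84 = 94.1%; raw specificity = 77.76/112.32 = 69.2%.
- Begg-Greenes applies the verified proportions to all MRA reads. Residual flow among MRA-positive: 273.6 × 184.32/218.88 = 230.4. Among MRA-negative: 446.4 × 11.52/89.28 = 57.6.
- Corrected sensitivity = 230.4/288 = 80%; corrected specificity = 388.8/432 = 90%.

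The recovery is exact because the example makes DSA depend only on the MRA result.

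**Site read against core-lab read.** The planned table uses core-lab classes, whereas a routine decision to add DSA would presumably follow the site's own reading. Suppose the two MRA readings agree in 85% of patients, regardless of true status. Verification of 80%/20% by site read becomes 0.85·0.80 + 0.15·0.20 = 71% and 0.85·0.20 + 0.15·0.80 = 29% by core-lab read. Raw accuracy is then about 91%/79% instead of 94%/69%.

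**The case against.** The strongest reply is that the premise is not in the documents. Protocol 6.9 sets no order and no trigger for a second scan. DSA may be a site's routine examination, may come first, or may be done whatever MRA shows. A reader might infer from the remark that "MRA imaging is safer for patients and less expensive" that DSA will mostly follow an abnormal MRA, and hence that the study will overstate MRA sensitivity. That sentence explains why the comparison is of interest; it does not say who gets a second scan. The inference is unsupported, and with equal verification this bias is absent.

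Three further points stand. The direction is not common to all planned targets, as Class II alone shows. If the site's reading drives the use of DSA, the bias in the core-lab table is diluted, and a correction that conditions only on core-lab class may not meet its missing-at-random assumption. And the analysis is descriptive, supports no endpoint, and Protocol 10.12 says openly which patients it uses.

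What does not stand is leaving the matter there. The documents do not rule selective verification out, and the plan as written would not let a reader tell whether it had occurred.

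**Conclusion.** The point holds as an unexamined risk in an analysis that serves a stated objective. If DSA is more frequent after a positive MRA, raw sensitivity for any residual flow is too high and raw specificity too low. From an assumed true 80%/90%, the raw result ranges from 83%/88% at 50%/40% verification to 94%/69% at 80%/20%. Those sizes rest on assumed accuracy and on DSA depending on the core-lab MRA class itself. They shrink if the site's reading is the driver, vanish under equal verification and reverse under the opposite pattern. The documents do not support saying that the bias will occur, or that it has a known direction for every target. The primary and secondary endpoints are not affected by this point. It merits a short SAP addition.

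**What to change.** In SAP 8.3:

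1. State that the raw estimates apply to patients who had both scans, and align the population wording with Protocol 10.12.
2. Report the number and share of patients in each core-lab MRA class who also had DSA. SAP 8.4 already plans counts of follow-up DSA and MRA scans.
3. As a sensitivity analysis beside the raw estimates, add Begg-Greenes corrected (or multiply imputed) sensitivity, specificity and likelihood ratios using all patients with a core-lab MRA read. Work by MRA class, so that all three Raymond-Roy targets are covered. Condition also on the site-reported occlusion grade and baseline covariates where available. The site grade should be used only where it is known to be the reading of the MRA, since in a patient with both scans it may reflect DSA.

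The cost is a short SAP text and some programming on data that Protocol 6.9 already asks sites to send. Protocol 7.5 words image upload less firmly, so MRA reads without DSA may be incomplete; a count of reads received would show this. The downside is that the correction assumes DSA is missing at random given the MRA class and the other variables used, which cannot be verified from the data, and its intervals are wider. If the shares in item 2 turn out equal, the raw result gains credibility at almost no cost.
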